# **15.2. Key Secondary Efficacy**

#### 15.2.1. Key Secondary Efficacy Variables & Derivations

#### 15.2.1.1. Change in CGI-S Score Between Baseline and Week 6

The severity of illness for each subject will be rated using the CGI-S. To perform this assessment, the rater or Investigator will answer the following question: "Considering your total clinical experience with this particular population, how mentally ill is the subject at this time?" Response choices include: 0 = not assessed; 1 = normal, not at all ill, 2 = borderline mentally ill; 3 = mildly ill; 4 = moderately ill; 5 = markedly ill; 6 = severely ill; and 7 = among the most extremely ill subjects.

Numerical values 1 through 7 corresponding to each response category (except "not assessed" category) will be used in analysis. The category of "not assessed" will be treated as a missing numerical value for analysis.

#### **15.2.2.** MISSING DATA METHODS FOR KEY SECONDARY EFFICACY VARIABLES

Missing data for the key secondary endpoint of change in CGI-S score between baseline and Week 6 will be treated in the same way as for the primary efficacy endpoint.

#### **15.2.3.** ANALYSIS OF KEY SECONDARY EFFICACY VARIABLES

Analysis of the key secondary efficacy endpoint will be performed for the Full Analysis Set with multiplicity adjustment as described in Section 7.4.

Change from Baseline in CGI-S score at Week 6 will be analyzed in the same way as described in Section 15.1.3 for the primary endpoint, with the only difference that the MMRMs will use Baseline value of CGI-S as covariate instead of Baseline PANSS total score.

Document:	\\quintiles.net\Enterprise\Apps\sasdata\SASb\SAS\Noven\HP-			
	3070\XWA17541\Biostatistics\Documentation\SAP\Final 6\Noven HP-3070-GL-04 SAP text Final			
	6_18Jan2018.docx			
Author:	[name]	Version Number:	Final 6	
		Version Date:	18Jan2018	
Template No: CS_TP_BS016 – Revision 3		Reference: CS_WI_BS005		

Copyright © 2012 Quintiles Transnational Corp. All rights reserved.

Noven Pharmaceuticals, Inc. STATISTICAL ANALYSIS PLAN: PROTOCOL HP-3070-GL-04 Page 30 of 50

Sensitivity analysis of the key secondary endpoint will be performed in the same way as described in Section 15.1.4 for the primary endpoint.

# **15.3. OTHER SECONDARY EFFICACY**

#### 15.3.1. EXPLORATORY EFFICACY VARIABLES & DERIVATIONS

15.3.1.1. Change from Baseline in PANSS Total Score at Weeks 1 through 5

PANSS total score will be calculated for each subject and time point as described in Section 15.1.1.

#### 15.3.1.2. Change from Baseline in CGI-S Score at Weeks 1 through 5

CGI-S scores at each time point will be assessed as described in Section 15.2.1.1.

#### 15.3.1.3. CGI-I Responder at Weeks 1 through 6

The efficacy of trial medication will be rated for each subject using the CGI-I. The rater or Investigator will rate the subject's total improvement whether or not it is due entirely to drug treatment. All responses will be compared to the subject's condition at Baseline prior to the first dose of double-blind study drug. Response choices include: 0 = not assessed, 1 = very much improved, 2 = much improved, 3 = minimally improved, 4 = no change, 5 = minimally worse, 6 = much worse, and 7 = very much worse. The category of "not assessed" will be treated as a missing numerical value for analysis. CGI-I responders are defined as subjects who have a score of 1 (very much improved) or a score of 2 (much improved).

#### 15.3.1.4. CGI-I Score at Weeks 1 through 6

Numerical values 1 through 7 corresponding to each CGI-I response category as described in Section 15.3.1.3 (except "not assessed" category) will be used in analysis. The category of "not assessed" will be treated as a missing numerical value for analysis. CGI-I score at each week will be analyzed in the same way as described in Section 15.1.3 for the primary endpoint, with the only difference that the MMRM will use Baseline value of CGI-S as covariate instead of Baseline PANSS total score.

#### 15.3.1.5. Change from Baseline in PANSS Positive Subscale at Weeks 1 through 6

PANSS Positive Subscale is a sum of 7 positive items: delusions, conceptual disorganization, hallucinatory behavior, excitement, grandiosity, suspiciousness/persecution, and hostility.

If one or more items in the subscale are missing at a given assessment, the subscale score will be set to missing.

#### 15.3.1.6. Change from Baseline in PANSS Negative Subscale at Weeks 1 through 6

PANSS Negative Subscale is a sum of 7 negative items: blunted affect, emotional withdrawal, poor rapport,

Document:	\\quintiles.net\Enterprise\Apps\sasdata\SASb\SAS\Noven\HP-		
	3070\XWA17541\Biostatistics\Documentation\SAP\Final 6\Noven HP-3070-GL-04 SAP text Final		
	6_18Jan2018.docx		
Author:	[name]	Version Number:	Final 6
		Version Date:	18Jan2018
Template No:	CS_TP_BS016 - Revision 3	Reference: (	S WL BS005

Effective Date: 01May2012

Copyright © 2012 Quintiles Transnational Corp. All rights reserved.

Noven Pharmaceuticals, Inc. STATISTICAL ANALYSIS PLAN: PROTOCOL HP-3070-GL-04 Page 31 of 50

passive/apathetic social withdrawal, difficulty in abstract thinking, lack of spontaneity and flow of conversation, stereotyped thinking.

If one or more items in the subscale are missing at a given assessment, the subscale score will be set to missing.

#### 15.3.1.7. Change from Baseline in PANSS General Psychopathology Subscale at Weeks 1 through 6

PANSS General Psychopathology Subscale is a sum of 16 items: somatic concern, anxiety, guilt feelings, tension, mannerisms and posturing, depression, motor retardation, uncooperativeness, unusual thought content, disorientation, poor attention, lack of judgment and insight, disturbance of volition, poor impulse control, preoccupation, and active social avoidance.

If one or more items in the subscale are missing at a given assessment, the subscale score will be set to missing.

# 15.3.1.8. PANSS Responder Based on ≥30% Improvement from Baseline in PANSS total score at Weeks 1 through 6

At each time point, subjects having a 30% or greater improvement from baseline in PANSS total score will be defined as "responders".

The PANSS total score percentage change will be defined as (Value at Week X – Baseline value) X 100 / (Baseline value).

The responder indicator will be set to 1 if the percentage change is less than or equal to -30% and set to 0 if the percentage change is greater than -30% or missing.

# 15.3.1.9. PANSS Responder Based on >=X% Improvement from Baseline in PANSS total score at Week 6

At Week 6, responder status will be derived in a similar way as described in section 15.3.1. 8 at different levels of required percent improvement from baseline where X=5% to 100% with 5% increments.

A continuous responder analysis will be performed based on these derivations as described in Section 15.3.3.3.

#### 15.3.1.10. Change from Baseline in CDSS Score at Weeks 1 through 6

The CDSS is a nine-item scale designed for assessment of the level of depression in patients with schizophrenia. Each of the 9 items is rated on a 4-point scale, scored from 0-3. The first 8 items are rated on the basis of responses during a semi-structured interview conducted by a qualified clinician. The ninth item (Observed Depression) is rated by evaluating signs and symptoms over the course of the interview.

The total score is derived by adding each of the 9 items together. Totals scores of 6 or more identifies the presence of treatment emergent depression predictive of major depressive episodes. If one or more items are missing at a given assessment, the total score will be set to missing.

Document:	\\quintiles.net\Enterprise\Apps\sasdata\SASb\SAS\Noven\HP-		
	3070\XWA17541\Biostatistics\Documentation\SAP\Final 6\Noven HP-3070-GL-04 SAP text Final		
	6_18Jan2018.docx		
Author:	[name]	Version Number:	Final 6
		Version Date:	18Jan2018
Template No:	CS_TP_BS016 – Revision 3	Reference: (	CS WI BS005

Effective Date: 01May2012

Copyright © 2012 Quintiles Transnational Corp. All rights reserved.

Noven Pharmaceuticals, Inc. STATISTICAL ANALYSIS PLAN: PROTOCOL HP-3070-GL-04 Page 32 of 50

#### 15.3.1.11. MSQ Subscale Scores at Weeks 2, 4, and 6

The MSQ is a single-item questionnaire used to assess the level of patient's satisfaction or dissatisfaction with the medication they are taking. Responses can range from Extremely Dissatisfied (1) to Extremely Satisfied (7).

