## 3. STUDY DESIGN

## **3.1. GENERAL DESCRIPTION**

This is a Phase 3, randomized, double-blind, placebo-controlled, in-patient, safety, and efficacy study to evaluate HP-3070 for the treatment of schizophrenia.

This study will consist of a Screening/placebo Run-in Period of 3 to 14 days, a 6-week double-blind Treatment Period and a 30 day Follow-up Period.

Subjects will be hospitalized at the Screening Visit and will remain hospitalized during the study. The subject may leave the hospital study for necessary personal business. Any subject who leaves the site must have an alcohol breathalyzer and urine drug tests when they return to the site.

After obtaining informed consent, each subject will be assigned a unique subject number. Eligible subjects will be hospitalized for the duration of the study. While undergoing screening procedures and waiting for results of laboratory tests, ECGs, and other assessments, the subject will start treatment with the single-blind placebo patch. The subject must have the single-blind placebo patch applied for a minimum of 3 days prior to being randomized into the double-blind Treatment Period. In addition, current antipsychotic and other prohibited medications will be washed out during the run-in period and must be completed prior to randomization into the double-blind treatment period. Details in regard to wash-out periods for specific drugs are summarized in Protocol Section 5.10.1. Subjects who have a decrease in PANSS total score ≥20% from Screening to Baseline or a PANSS total score <80 at Screening or Baseline will be discontinued from the study and will not enter the double-blind Treatment Period.

Document:	\\quintiles.net\Enterprise\Apps\sasdata\SASb\SAS\Noven\HP-			
Documenti	3070\XWA17541\Biostatistics\Docu	imentation\SAP\Final 6\Noven HP-3070-GL-04 S/	AP text Final	
	6_18Jan2018.docx			
Author:	[name]	Version Number:	Final 6	
		Version Date:	18Jan2018	
Template No:	CS TP BS016 – Revision 3	Reference: C	CS WI BS005	

Effective Date: 01May2012

Copyright © 2012 Quintiles Transnational Corp. All rights reserved.

Noven Pharmaceuticals, Inc. STATISTICAL ANALYSIS PLAN: PROTOCOL HP-3070-GL-04 Page 12 of 50

Subjects eligible for randomization into the double-blind Treatment Period will be randomly assigned to HP-3070 9.0 mg, HP-3070 18.0 mg, or placebo in a 1:1:1 ratio stratified by country. Subjects will receive treatment with study medication daily for 6 weeks.

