## **15. EFFICACY OUTCOMES**

#### **15.1. PRIMARY EFFICACY**

#### **15.1.1. PRIMARY EFFICACY VARIABLE & DERIVATION**

The primary efficacy endpoint is the change in PANSS total score between Baseline and Week 6.

The PANSS consists of 3 subscales containing a total of 30 items. For each item, severity is rated on an anchored 7-point scale, with a score of 1 indicating the absence of symptoms and a score of 7 indicating extremely severe

Document:	\\quintiles.net\Enterprise\Apps\sasdata\SASb\SAS\Noven\HP-		
	3070\XWA17541\Biostatistics\Documentation\SAP\Final 6\Noven HP-3070-GL-04 SAP text Final		
	6_18Jan2018.docx		
Author:	[name]	Version Number:	Final 6
		Version Date:	18Jan2018
Template No:	CS_TP_BS016 – Revision 3	Reference: 0	CS_WI_BS005

Effective Date: 01May2012

Copyright © 2012 Quintiles Transnational Corp. All rights reserved.

Noven Pharmaceuticals, Inc. STATISTICAL ANALYSIS PLAN: PROTOCOL HP-3070-GL-04 Page 26 of 50

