#### symptoms.

The PANSS total score is the sum of all 30 items. The score ranges from 30 through 210, with higher values representing greater severity of illness.

If one or more items are missing at a given assessment, the total score will be set to missing.

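### PANSS percent improvement is divided by the raw baseline although the scale starts at 30, so the top responder thresholds cannot be reached and the 30% cut means 48% of the reducible score at baseline 80 and 35% at the scale maximum

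*SAP*

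**What the plan says.** Section 15.1.1 rates each of the 30 PANSS items on a 7-point scale, "with a score of 1 indicating the absence of symptoms", and gives the range of the total: "The score ranges from 30 through 210, with higher values representing greater severity of illness".

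Section 15.3.1.8 gives the derivation: "percentage change will be defined as (Value at Week X – Baseline value) X 100 / (Baseline value"). It then fixes the cut: "The responder indicator will be set to 1 if the percentage change is less than or equal to -30" per cent. The scale minimum is not subtracted here or anywhere else in the SAP.

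Section 15.3.1.9 reuses this derivation at Week 6 for a series of thresholds, "where X=5% to 100% with 5% increments". Section 15.3.3.3 plots and tabulates them, and Section 15.1.4 names the result as sensitivity Scenario #2 for the primary endpoint.

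The lowest possible baseline follows from Section 3.1: "a PANSS total score <80 at Screening or Baseline will be discontinued from the study". No upper limit is stated.

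Scenario #3 in Section 15.1.4 (time to failure) also uses a percent improvement, with a 20% cut, but names no denominator.

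**The concern.** A percentage of baseline has its plain meaning only if zero on the scale means no symptoms. On the PANSS total that point is 30. Dividing by the raw baseline counts 30 points that no treatment can remove.

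This has two consequences. First, complete absence of symptoms never registers as 100%, so part of the planned curve and table shows zero in every arm because of the formula. A reader may take those rows as a finding about the drug. Second, the same nominal 30% asks for a different share of the removable score at each baseline, and is strictest for the least ill. The responder test in Section 15.3.3.2 is stratified by country only, so it does not take up that dependence.

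**Working it through.** **Inputs, all from the SAP except one.** 30 items scored 1 to 7 (Section 15.1.1); raw-baseline denominator and 30% cut (15.3.1.8); thresholds 5% to 100% in steps of 5, which is 20 thresholds (15.3.1.9); lowest baseline 80 (3.1); 20% time-to-failure cut (15.1.4). Assumption: 120 stands for a high baseline, since the SAP gives no maximum. The scale limit of 210 is shown as the outer bound.

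**The plan's own figure.** 30 × 1 = 30 and 30 × 7 = 210, which reproduces the stated range.

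**Formulas at baseline B.**
- Reducible score: B − 30.
- Largest improvement the plan's formula can return: (B − 30)/B.
- Points needed for 30% as written: 0.30 × B.
- The same points as a share of the reducible score: 0.30 × B/(B − 30).
- Points needed for 30% of the reducible score: 0.30 × (B − 30).

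| Baseline B | Largest improvement | Points for 30% as written | Share of reducible score | Points for 30% of reducible score |
|---|---|---|---|---|
| 80 | 50/80 = 62.5% | 24 | 24/50 = 48.0% | 15 |
| 100 | 70/100 = 70.0% | 30 | 30/70 = 42.9% | 21 |
| 120 (assumed) | 90/120 = 75.0% | 36 | 36/90 = 40.0% | 27 |
| 210 (scale limit) | 180/210 = 85.7% | 63 | 63/180 = 35.0% | 54 |

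**Unreachable thresholds.** A threshold t can be met only if (B − 30)/B ≥ t, that is, B ≥ 30/(1 − t).
- t = 90%: B ≥ 30/0.10 = 300, above the scale maximum of 210.
- t = 95%: B ≥ 30/0.05 = 600.
- t = 100%: no finite baseline.

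These three thresholds are empty at every baseline. At baseline 80 every threshold from 65% up is unreachable (8 of 20). At 120 every threshold from 80% up is unreachable (5 of 20).

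**Time to failure.** If Scenario #3 borrows the raw denominator, its 20% cut equals 0.20 × 80/50 = 32.0% of the reducible score at baseline 80 and 0.20 × 120/90 = 26.7% at 120. This is conditional, because Section 15.1.4 does not say which denominator applies. The shells also disagree on the cut. Tables 14.2.1.2.3 and 14.2.1.2.4 (PANSS) and 14.2.2.5 and 14.2.2.6 (CGI-S) use 20%. The Pattern 3 tables, 14.2.1.2.5 and 14.2.2.7, use 30%.

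**The case against.** The formula is explicit, and it is a literal reading of the objective in Section 2.3, a 30% improvement from baseline. Changing the denominator redefines a secondary endpoint and loses direct comparability with trials that used the raw form. That cost is real. But Section 2.3 gives no formula, so a floor-corrected derivation fits it too, and the raw rate can be kept as a supplementary row.

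The reach is limited, and this stands in full. The outputs are other-secondary or sensitivity analyses without multiplicity adjustment (Section 7.4). The primary and key secondary MMRMs use absolute change. A reader might infer that the randomised comparison is biased. It is not, because every arm gets the same formula.

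A reader might also infer that the raw denominator hides part of the treatment effect, since removing the floor can widen the difference in responder rates. The documents do not support that. At a single baseline, changing the denominator only moves the bar: at 95 it goes from 0.30 × 95 = 28.5 points to 0.30 × 65 = 19.5, the same as a raw cut of 19.5/95 = 20.5%. Any change in the difference comes from that easier threshold.

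The continuous analysis already has a raw 20% row, close to a floor-corrected 30% (raw 18.8% at baseline 80, 22.5% at 120). This helps at Week 6 only, and that row still varies with severity. The empty rows carry no p-value in the shell for Table 14.2.3.7, so they mislead about the size of response, not about a test.

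**Conclusion.** The point holds within limits. The stated formula yields a percentage that depends on baseline severity, and the plan schedules three thresholds that no subject can reach. The ceilings of 62.5% at baseline 80 and 85.7% at 210, and the 30% cut's equivalents of 48% and 35% of the reducible score, follow from the SAP alone. The 40% figure rests on an assumed baseline of 120, so a range of 40% to 48% should not be read as the plan's own.

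What is affected is the meaning, size and comparability of the responder rates in Section 15.3.1.8 and of Scenario #2. Scenario #3 is affected only if it uses the same denominator, which is unstated. The sample size, the multiplicity procedure and the primary and key secondary MMRM results do not depend on this.

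**What to change.** Before unblinding:

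1. In Sections 15.3.1.8 and 15.3.1.9, define percent change as (Value − Baseline) × 100/(Baseline − 30). Align Tables 14.2.3.5 to 14.2.3.8 and Figures 14.2.3.7 and 14.2.3.8.
2. Keep the raw-denominator rate as a labelled supplementary row.
3. State the denominator for Scenario #3: (Baseline − 30) for PANSS and (Baseline − 1) for the CGI-S version, whose analysed values start at 1 (Section 15.2.1.1). Changing PANSS alone would leave two kinds of percentage inside one scenario.
4. Reconcile the 20% cut in Section 15.1.4 with the 30% cut in Tables 14.2.1.2.5 and 14.2.2.7.
5. If the protocol itself specifies the raw formula, record the change in Section 3.3, which now reports none.

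The cost is a short edit to the derivations and several shells, with no new data. The downside is that the main rates would not compare directly with trials using the raw denominator. They would also rest on a lower bar in points (15 instead of 24 at baseline 80), so the report should say which definition each rate uses.

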#### 15.3.2. MISSING DATA METHODS FOR OTHER SECONDARY EFFICACY VARIABLES

For continuous variables, missing data will be handled in the same way as for the primary efficacy endpoint.

For responder-type endpoints, subjects with missing data at a given time point will be classified as non-responders at that time point.

#### 15.3.3. ANALYSIS OF OTHER SECONDARY EFFICACY VARIABLES

All other secondary efficacy endpoints will analysed for the Full Analysis Set.

#### 15.3.3.1. Other Secondary Efficacy Endpoints Based on Continuous Variables

All endpoints based on continuous variables (all except PANSS responder endpoints based on percentage improvement) will be analyzed in the same way as described in Section 15.1.3 for the primary endpoint, with the only difference in that the MMRM models will use Baseline value of the corresponding efficacy variable as covariate instead of Baseline PANSS total score.

#### 15.3.3.2. Other Secondary Efficacy Endpoints Based on Binary (Responder) Variables

Effect of treatment on the proportion of PANSS responders from Baseline in PANSS total score as well as on the proportion of CGI-I responders at Weeks 1 through 6 will be tested using the Cochran Mantel Haenszel (CMH) method stratified by country. The hypothesis test will be based on the General Association statistic.

Descriptive summaries will be provided for the number and percentage of responders at Weeks 1 through 6 by treatment group. Also, estimates of the proportion of responders in each treatment group and differences of proportions (risk difference) between the treatment groups will be provided using the standard method based on the binomial distribution. Two-sided 95% CIs for proportion estimates based on the Wilson method and 2-sided 95% CIs for risk differences based on the Newcombe method will be reported.

#### 15.3.3.3. PANSS Continuous Responder Analysis at Week 6

A continuous responder analysis will be performed based on definition of responder at multiple levels of percent improvement from Baseline, from 5% to 100% with 5% increments. Results will be reported by means of a graph with response threshold on the X-axis and proportion of responders in each treatment group on the Y-axis. Corresponding data will be presented in a summary table.

Document:	\\quintiles.net\Enterprise\Apps\sasdata\SASb\SAS\Noven\HP-		
	3070\XWA17541\Biostatistics\Documentation\SAP\Final 6\Noven HP-3070-GL-04 SAP text Final		
	6_18Jan2018.docx		
Author:	[name]	Version Number:	Final 6
		Version Date:	18Jan2018
Template No:	CS TP BS016 – Revision 3	Reference: 0	CS WI BS005

Effective Date: 01May2012

Copyright © 2012 Quintiles Transnational Corp. All rights reserved.

Noven Pharmaceuticals, Inc. STATISTICAL ANALYSIS PLAN: PROTOCOL HP-3070-GL-04 Page 33 of 50

## **16.** SAFETY OUTCOMES

All outputs for safety outcomes will be based on the Safety Analysis Set.

There will be no statistical comparisons between the treatment groups for safety data, unless otherwise specified within the relevant section.

# **16.1. TREATMENT EMERGENT ADVERSE EVENTS**

Adverse events will be coded using MedDRA central coding dictionary, version 20.1 . Severity for AEs is classified in the eCRF as 'mild', 'moderate', or 'severe'.

Treatment Emergent Adverse Events (TEAEs) are defined as AEs that first occurred or worsened in severity after the first administration of the study drug.

TEAEs during the double-blind treatment period is defined as an AE with a start date on or after the date of first dose of double-blind study medication through the 30 day follow-up period. The same rule applies for Run-in Period (for those enrolled in the double-blind period)

SAEs that occur within 30 days after last dose of double-blind study medication will be reported.

In the case where it is not possible to define an AE as treatment-emergent or not, the AE will be classified by the worst case i.e. treatment-emergent.

Adverse event summaries will include numbers of events and subject incidence (number and percentage of subjects with at least one event) by treatment group and further categorization as described below.

An overview of AEs within each of the categories described below will be provided:

- AEs (for those who enrolled in the double-blind period) which occurred during the single-blind run-in or double-blind period
- TEAEs
- TEAEs by highest severity
- TEAEs by strongest relationship to study medication (Not Related, Related)
- TEAEs leading to study medication discontinuation
- Serious TEAEs
- Serious TEAEs by strongest relationship to study medication (Not Related, Related)
- TEAEs leading to death
- Commonly occurring TEAEs (defined as those which occur in 5% or more of the subjects in any treatment arm)
- TEAEs at the patch application site

Document:	\\quintiles.net\Enterprise\Apps\sasdata\SASb\SAS\Noven\HP-		
	3070\XWA17541\Biostatistics\Documentation\SAP\Final 6\Noven HP-3070-GL-04 SAP text Final		
	6_18Jan2018.docx		
Author:	[name]	Version Number:	Final 6
		Version Date:	18Jan2018
Template No:	CS_TP_BS016 - Revision 3	Reference: (	S WL BS005

Effective Date: 01May2012

Copyright © 2012 Quintiles Transnational Corp. All rights reserved.

Noven Pharmaceuticals, Inc. STATISTICAL ANALYSIS PLAN: PROTOCOL HP-3070-GL-04 Page 34 of 50

Multiple occurrences of the same category of AEs will be counted once for each subject, at the highest severity and strongest relationship to study medication as appropriate.

Listings will include all AEs (TEAEs and non-TEAEs) collected on the eCRF for each study period based on the onset date.

The following algorithm will apply to partial dates. Imputed dates will NOT be presented in the listings but may be used to determine treatment-emergent status of AEs and category of medications (prior, concomitant, or post-treatment).

If an adverse event, as reported on the eCRF, has a partially or completely missing event start or end date, use the following algorithm to impute missing components of the date(s). Imputed dates will be used in order to determine treatment-emergent status of an AE as well as to assign the AE to one of the treatment periods.

Let AESTDTC represent the AE start date and AEENDTC represent the AE stop date.

If an AE has some missing components in both the start and end dates, first impute the end date as follows (only if AE is not ongoing):

- 1. If AEENDTC contains only year and month impute the missing day to the last day of the corresponding month (e.g., 31 for January, or 30 for April).
- 2. If AEENDTC contains only year impute the missing day and month to the 31st of December of the corresponding year.
- 3. If AEENDTC is completely missing impute to the date of the last contact with the subject.

Note: AE end date should remain null for AEs that are ongoing.

After having imputed the AE end date (if needed), impute the AE start date if it is partial or missing as follows: 1. If AESTDTC contains only year and month

- 1.1 If AESTDTC = year-month part of the first dose date of study medication:
  - 1.1.1 If AE is not ongoing impute to the earlier of the first dose date of double-blind study
    - medication and AE end date (previously imputed if needed).
    - 1.1.2 If AE is ongoing impute to the first dose date of double-blind study medication.
- 1.2 If AESTDTC ≠ year-month part of the first dose date of double-blind study medication, impute the missing day to the first day of the month.
- 2 If AE start date contains only year
  - 2.1 If AESTDTC = year part of the first dose date of double-blind study medication:
    - 2.1.1 If AE is not ongoing impute to the earlier of the first dose date of double-blind study medication and AE end date (previously imputed if needed).
    - 2.1.2 If AE is ongoing impute to the first dose date of double-blind study medication.
  - 2.2 If AESTDTC ≠ year part of the first dose date of double-blind study medication impute to January 1st of the year in AESTDTC.
- 3 If AE start date is completely missing
  - 3.1 If AE is not ongoing impute to the earlier of the first dose date of double-blind study medication and AE end date (previously imputed if needed).

Document:	\\quintiles.net\Enterprise\Apps\sasdata\SASb\SAS\Noven\HP-		
	3070\XWA17541\Biostatistics\Documentation\SAP\Final 6\Noven HP-3070-GL-04 SAP text Final		
	6_18Jan2018.docx		
Author:	[name]	Version Number:	Final 6
		Version Date:	18Jan2018
Template No:	CS_TP_BS016 - Revision 3	Reference: (	S WL BS005

Effective Date: 01May2012

Copyright © 2012 Quintiles Transnational Corp. All rights reserved.

If AE is ongoing – impute to the first dose date of double-blind study medication.

